### 5.2 Contraindications

Definity should not be administered to patients with known or suspected hypersensitivity to perflutren. The safety of Definity in patients with 1) right-to-left, bi-directional or transient right-to-left cardiac shunts; 2) severe emphysema, pulmonary vasculitis or a history of pulmonary emboli; 3) confirmed or suspected severe liver lesions; and 4) respiratory distress syndrome has not been studied. Therefore, patients with any of these conditions will be excluded from the participation.

### 5.3 Randomization

This is a non-randomized trial; therefore, no randomization procedure is required.

#### 5.4 Blinding and Unblinding Methods

This is an open-label trial; therefore, no blinding or unblinding procedures for the trial drug are required.

#### 5.5 Storage

Definity vials will be stored in a secure refrigerator, with only the study investigators and research personnel having access. The study research nurse will be responsible for drug suspension and inventory control.

### 6. TRIAL PROCEDURES

#### 6.1 Patient Enrollment and Consent

Subjects eligible for trial enrollment will be identified by the investigators from among TJU and UCSD's patient population who are referred for a breast biopsy. An investigator or research coordinator will explain the study to the patient. The patient will be given time to consider the risks and benefits of the study and ask questions about participation. The consent form will be reviewed with the patient and then the patient will be given the form to review. If consent interview is conducted by a coordinator, a study investigator will then discuss the study with the subject and answer any additional questions. The patient, person conducting study interview (if applicable), and a study investigator will all sign the consent form. The patient will be given a copy of the signed consent form for her records.

#### 6.2 Screening Assessments

Screening assessments will be performed within 24 hours prior to the administration of Definity. Trial participants will have the presence of inclusion criteria and absence of exclusion criteria verified by providing a medical history. A full demographic profile, known drug allergies or intolerances, and a review of the subject's medical/surgical history will be recorded. If the subject is a woman of childbearing potential, she will have a urine pregnancy test (the results of which will be made available to the subject prior to study initiation).

#### 6.3 Ultrasound Imaging

The US examinations will be performed by a qualified sonographer. Procedures and equipment for this trial will be used in accordance with typical clinical procedures. In particular, the mechanical index will be set to less than 0.8 on the US scanner. All trial procedures will be conducted in accordance with Good

Clinical Practice. For the ultrasound examination, the patient will be asked to lie in the supine position and a catheter will be placed in a superficial vein (preferably an antecubital vein). Acoustic coupling gel will be applied to the breast area of interest. A baseline US grayscale scan will be used to identify the mass or abnormal area seen by mammography (or another concomitant imaging mode such as US or MRI). Standard PDI of the lesion or target area will also be performed.

Following baseline imaging, patients will receive a bolus, IV injection of 0.25 ml of Definity and the mass or area of abnormality will be imaged with the broad bandwidth linear array (selected in the development phase described above) and a 30 to 40 second digital clip of the 3D pulse inversion HI volume data, covering baseline to beyond peak enhancement, will be acquired. The point of maximum enhancement in the pulse inversion harmonic images will be assessed visually (by the on-site investigators in consensus) and at least 10 seconds of data will be acquired past this time point. Subsequently more sweeps of the abnormality will be stored on the scanner hard drive every 1 to 2 minutes through the period of enhancement (up to 5 minutes).

After a 30 minutes waiting period patients will receive a second bolus, IV injection of up to 20  $\mu$ l/kg of Definity, sweeps of the mass or abnormal area will be made to acquire 3D SHI grayscale volume data through the period of enhancement (up to 2 minutes in our pilot study). It should be noted, that all subjects will be closely monitored by a physician during and following the study (for 30 minutes as recommended by the FDA) [FDA Alert 2007/2008]. Additionally, resuscitation equipment and trained personnel will be in immediate proximity to the patient during the study.

All images (baseline and contrast-enhanced) will be obtained using a broad bandwidth, 3D, linear array, and will include images of the entire area of interest. The entire examination will be recorded as digital loops, as well as on VHS videotape.

#### 6.4 Safety Monitoring

Patients will be monitored for AEs during and 30 mins after contrast administration. All other procedures will be performed according to TJU/UCSD standard of care.

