#### Definity Clinical Safety

Definity is well tolerated and has been used extensively in echocardiography applications [Goldberg et al 2001]. In pre-market clinical trials, Definity was administered to 1716 patients. In these patients 269 (8.4%) reported at least one adverse event. Of these events, 26 were classified as serious including 19 (1.1%) patients experiencing serious cardiopulmonary symptoms including eight deaths. The deaths occurred several days after activated Definity administration and appear to be related to the course of underlying disease. Of the 11 other serious adverse events, which appeared within days of the drug administration (2-15 days), all appeared to be a progression of underlying cardiac and non-cardiac disease. However, a role for Definity in the initiation or course of these adverse events can not be ruled out.

Of the reported adverse reactions following the use of Definity the most frequently reported were headache (2.3%), back and renal pain (2.1%), flushing (1.1%), and nausea (1.0%). Additional risks associated with the contrast material are described in the attached Definity Product insert (Appendix B). All of the non-serious reported side affects have been transient, usually lasting only a few minutes.

Table 1.

Selected Adverse Events Reported in  $\geq 0.5\%$  of the Subjects who Received Definity in Controlled Clinical Studies

No. of Patients Exposed to Definity	1716
No. of Patients Reporting an Adverse Event	269 (8.8%)
Central and peripheral nervous system	54 (3.2%)
Headache	40 (2.3%)
Dizziness	11 (0.6%)
Body as a Whole	41 (2.4%)
Back/Renal Pain	20 (1.2%)
Chest Pain	13 (0.8%)
Digestive System	31 (1.8%)
Nausea	17 (1.0%)
Vascular (extracardiac) disorders	19 (1.1%)
Flushing	19 (1.1%)
Application Site Disorders	11 (0.6%)
Injection Site Reactions	11 (0.6%)

Additional information concerning pre-clinical and clinical experience with Definity, including the dosing levels and reported subject complaints, can be found in the Definity Package Insert that is included as Appendix B.

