### 3.1 Trial Duration

Individual participation in this trial will be limited to US imaging studies (baseline and contrast-enhanced) and a breast biopsy performed up to 30 days after the US study procedures. Baseline and contrast-enhanced images will be acquired on the same day. The entire imaging protocol will require approximately two hours. Subject recruitment is expected to last 3 years (June 2011-2014).

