### 6.8.1 Risks/Benefits Assessment.

Serious cardiopulmonary and allergic reactions including fatalities have occurred during or following administration of Definity, causing the FDA to place a black box warning on the agent. However these occurrences have been rare (less than 1 in 5,000 patients). As a result, patients with cardiac shunts or unstable cardiopulmonary conditions will be excluded. Patients will also be monitored for 30 minutes after contrast administration for any adverse reactions. The majority of adverse events from Definity were mild to moderate in severity. Transient side effects that have been described as possibly related to Definity administration include headache (2.3%), back and renal pain (2.1%), flushing (1.1%) and nausea (1.0%). Hypersensitivity reactions to perflutren may occur, although rare.

The use of an intravenous needle and the fluids given through the needle may cause minor discomfort, bleeding under the skin (bruise), and possible infection at the site of needle insertion.

Clinically significant adverse effects from the administration of Definity are unlikely. The use of contrast with the new US imaging techniques is expected to provide significantly more information than from conventional US techniques. This may lead to additional information about the characteristics of breast tumors which may be clinically relevant.

To minimize and/or eliminate risks a nurse will be present during the entire procedure. Adverse events will be monitored during the entire procedure.

The risk benefit ratio is low. Based on the available non-clinical and clinical safety data and the anticipated dose levels of Definity that will be used in this study, safety concerns are minimal. The potential side effects related to Definity administration are described above. In a relatively healthy outpatient population referred for surgical breast biopsy we do not expect any severe reactions. However, in order to ensure that the 20  $\mu$ l/kg dose used for SHI is not altering the risk benefit ratio, data from the first ten (10) patients and then the next ten patients (i.e., the first 20 subjects) will be scrutinized by the TJU DSMB immediately upon completion. If AEs are encountered to a higher degree than what is expected given the Definity label, the dosing will be adjusted downward.

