#### 6.8.2 Adverse Events

An AE includes any condition that was not present prior to trial treatment, but appeared following initiation of trial medication; any condition that was present prior to trial treatment, but worsened during trial medication; or any condition, of which the subject has a history, that was not present prior to trial medication initiation but reappeared following administration of Definity. This would include conditions that are likely to be associated with an underlying or intermittent disease (e.g., angina, flu, etc.).

The subjects will be monitored for AEs during the entire procedure. All AEs, including both observed or volunteered problems, complaints, signs or symptoms, and diagnoses, occurring from the initiation of Definity dosing until the completion of the Definity administration will be recorded on a serious or non-serious AE data form, whether or not associated with the use of the trial medication. All adverse events are reported to the Clinical Research Management Office (CRMO) via the password protected Kimmel Cancer Center Adverse Event Reporting System. In addition all unexpected and serious adverse events (SAEs) are reported to the TJU IRB and to the Food and Drug Administration (FDA) if applicable. The investigator is required to submit all unexpected and serious adverse events to the TJU IRB and the DSMB within 48 hours. Fatal adverse events related to treatment which are unexpected must be reported

within 24 hours to the TJU IRB and the DSMB through CRMO. Fatalities not related to the study drug/device must be reported within 5 days.

The AE forms will include: subject identification number and initials; subject's date of birth, gender, and ethnicity; date of Definity administration; signs/symptoms and severity; date of onset; date of resolution or death; relationship to the study drug; action taken; concomitant medication(s) including dose, and route and duration of treatment.

Whenever possible, the AE will be evaluated and reported as a diagnosis rather than individual signs and symptoms. If a definitive diagnosis is not possible, the individual signs and symptoms will be recorded. The investigator will evaluate and note the duration, intensity, and relationship to (association with) the Definity administration, the action taken, and the determination of seriousness for each AE.

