#### SERIOUS ADVERSE EVENTS

A "serious" AE (SAE; Grades 3-5) is defined as a significant clinical hazard, contraindication, or precaution that:

- Results in death
- Is life-threatening (In the opinion of the investigator, there is an immediate risk of death from the AE as it occurred. This does not include an AE that had it occurred in a more serious form may have caused death.)
- Results in a persistent or significant temporary disability/incapacity defined as a substantial disruption of a person's ability to conduct normal life functions
- Results in or prolongs an existing in-patient hospitalization (an overnight stay in the hospital, regardless of length) [Note: A hospitalization for an elective procedure or treatment which is not associated with an AE, hospitalization for a pre-existing condition which did not worsen, and hospitalization for reasons of convenience or observation, do not constitute an SAE.]
- Is a congenital anomaly/birth defect (in offspring of a subject taking the trial medication, regardless of time to diagnosis)
- Is an important medical event that may not result in death, be life-threatening, or require hospitalization but based upon the appropriate medical judgment, the event may jeopardize the subject and may require medical or surgical intervention to prevent one of the outcomes listed for the definition of a serious adverse experience.

All unexpected and serious adverse events are reported to the TJU/UCSD IRB and to FDA if applicable. The investigator is required to submit all unexpected and serious adverse events to the TJU/UCSD IRB

and the data safety monitoring board within 48 hours. Fatal adverse events related to treatment which are unexpected must be reported within 24 hours to the TJU/UCSD IRB and the DSMB through CRMO.

The written report for any SAEs that occur during the study, whether or not related to the Definity administration will be submitted immediately (within 24 hours) to the TJU (or UCSD) Institutional Review Board.

The designated medical monitor will review all serious and unexpected adverse events associated with the protocol and provide an unbiased written report of the event within 10 calendar days of the initial report. At a minimum, the medical monitor will comment on the outcomes of the adverse event and relationship of the event to the Definity administration.

A copy of the SAE will be retained on file with the respective subject's data forms.

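### No safety ascertainment is scheduled between 30 minutes after contrast and biopsy up to 30 days later, although any SAE during the study must be reported

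*Combined protocol and SAP*

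**What the plan says.** Three places give three windows for safety events.

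- **Section 6.4:** "Patients will be monitored for AEs during and 30 mins after contrast administration". Sections 6.3 and 6.8.1 repeat the 30 minutes, and 6.3 bases it on an FDA recommendation.
- **Section 6.8.2, recording:** AEs "from the initiation of Definity dosing until the completion of the Definity administration will be recorded on a serious or non-serious AE data form". This window closes before the one in 6.4.
- **Section 6.8.2, Serious Adverse Events:** "The written report for any SAEs that occur during the study, whether or not related to the Definity administration" goes to the IRB within 24 hours. Hospitalization counts as serious. Section 6.8.2 also sets a 5-day deadline for unrelated deaths.

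Under 3.1, participation covers the imaging and "a breast biopsy performed up to 30 days after the US study procedures". At biopsy, 6.5 and 6.7 have the date and the pathology recorded. The completion criteria in 6.9.1 are two injections, the full imaging study and the biopsy; none is a safety check.

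On the timing of past serious events, section 1.1 (Definity Clinical Safety) says: "The deaths occurred several days after activated Definity administration". It describes 11 other serious events "which appeared within days of the drug administration (2-15 days"). It relates both groups to underlying disease, but adds that Definity may still have played a part. Section 6.8.1 lists "possible infection at the site of needle insertion" among the risks.

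**The concern.** The reporting duty covers the whole of participation, while planned ascertainment covers the imaging visit. The serious events whose timing the protocol gives fall in between. A patient admitted to another hospital on day 5 and biopsied on day 20 would meet every completion criterion, and no planned step would bring the admission to light. A needle-site infection would not be expected to show within 30 minutes either.

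What is at stake is how an absence of delayed events can be read. The trial uses Definity off-label under an IND and gives up to two injections. Section 6.8.1 has the DSMB look at the first 10 and then the next 10 patients, to see whether AEs exceed what the label leads one to expect. The pre-market experience described in 1.1 reaches to day 15, while the data planned for that look stop at the imaging visit. The comparison of serious events therefore leans towards reassurance. This holds whether a patient's completion means the end of imaging or the biopsy, because no safety question is asked at either point after the 30 minutes.

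**Working it through.** **1. Reproduce the stated rate (section 1.1).** Serious cardiopulmonary cases: 19/1716 = 1.107%, which rounds to the stated 1.1%.

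**2. Which events have a stated time?** 19 − 8 deaths = 11, which matches the 11 other serious events. The section counts 26 serious events, so 26 − 19 = 7 have no stated timing (the 26 are events and the 19 are patients, so the 7 is approximate). For the 11, a 2-15 day appearance lies outside a 30-minute window. For the 8 deaths, the text times the death, not the onset of the event that led to it.

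**3. Compare the windows.** 30 minutes is 0.5 h. Against 15 days: 0.5/360 = 0.14%. Against 30 days: 0.5/720 = 0.07%.

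**4. Illustrate the size.** Assumption: the pre-market rate p, or a fraction of it, applies here. Expected count = 450 × p; chance of at least one = 1 − (1 − p)^450.

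| Share of pre-market rate | All 19 (1.11%): expected; P(≥1) | The 11 at 2-15 days (0.64%): expected; P(≥1) |
|---|---|---|
| 100% | 5.0; 99% | 2.9; 94% |
| 50% | 2.5; 92% | 1.4; 76% |
| 25% | 1.2; 71% | 0.7; 51% |
| 10% | 0.5; 39% | 0.3; 25% |

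The documents do not give the fraction that applies to this population.

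**5. DSMB look.** For 20 patients at the full rate, 20 × 0.01107 = 0.22 cases are expected and P(≥1) = 20%. A look made straight after imaging could precede a day 2-15 onset.

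**6. What complete ascertainment would buy.** With zero events in 450 patients who were all checked, the one-sided 95% upper limit is 1 − 0.05^(1/450) = 0.66%. Without a check, no such limit can be stated, because the number of patients actually observed is unknown.

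**The case against.** The best defence is that the 30 minutes is a reasoned choice. It follows an FDA recommendation, in a diagnostic study whose objectives all concern imaging. Section 1.1 attributes the delayed events to underlying disease, 4.2 excludes unstable patients, and 6.8.1 describes a fairly healthy outpatient group. There is no control arm, and biopsy or surgery falls in the same 30 days, so late events would be hard to attribute. All of this stands, and it limits how much the data could show. But a recommendation on observing the patient does not settle how long SAEs are ascertained, and the protocol itself sets the longer reporting duty.

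A reader might infer four stronger things that the documents do not support.

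- **The trial cannot observe delayed events.** It can, passively. The SAE rules cover any SAE the site hears of, unrelated deaths have a deadline, and 6.9.1 records the reason for discontinuation, so a death or admission that prevents biopsy would leave a trace.
- **The SAE reporting duty cannot be met.** It can be met for every event that comes to the site's notice. Incomplete ascertainment does not make the duty impossible.
- **All 19 past cases, or all serious events, fell outside 30 minutes.** This is firm only for the 11.
- **The expected count runs from about 0.1 to 5.** The lower figure (450/5000 = 0.09) uses the rate in 6.8.1 for serious reactions during or following administration. That is not a rate of delayed events, so the two figures are not ends of one range.

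**Conclusion.** The point holds as a gap in scheduled ascertainment and as an internal inconsistency. Safety inquiry ends at 30 minutes (6.4), AE recording at the end of administration (6.8.2), and SAE reporting runs through the study (Serious Adverse Events). These must be reconciled. As written, delayed SAEs depend on passive report, and delayed non-serious AEs fall outside the recording window altogether.

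The gap follows from the text and does not depend on any event rate. The expected counts, about 5 at the full pre-market rate and 0.5 to 2.5 at 10-50% of it, rest on carrying a pre-market rate into a probably healthier group and are illustrations only. None of this shows that Definity causes delayed harm. The change should be made because it is cheap, and because the safety statement in the final report would otherwise lack a known denominator for events after the imaging visit.

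**What to change.** 1. Reconcile the windows in 6.4, 6.8.2 and the SAE rules. State one period for SAE ascertainment, extending to the end of participation, and use it on the AE form.
2. In 6.4 and 6.5, when the biopsy date and pathology are collected, also check the record for any hospital admission, death, other SAE or needle-site complication since the injections. Ask the patient as well if she is seen.
3. Enter either none or the event, with its date relative to the injections and to the biopsy.
4. Report these events separately from on-day AEs, with the number of patients checked. State whether the DSMB review of the first 20 patients includes them.
5. Optional: a later record check where biopsy falls before day 15, since participation would otherwise end inside the 2-15 day range.

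This changes data capture only; dosing, observation and care stay as they are. The cost is one added item at a data collection step that already takes place. A routine interview or separate call would cost more, because the protocol describes no coordinator contact at biopsy. The downside is that biopsy- and surgery-related events will also be collected, which is why each event needs both dates, and attribution stays limited without a control arm.

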#### 6.5 Surgical Biopsy

All subjects will be scheduled to undergo a breast biopsy (core / excisional / lumpectomy) of the mass or region of abnormality or mastectomy within 30 days after the US study procedure. The date of the

biopsy and the pathology results will be recorded. An experienced pathologist will complete a worksheet for each biopsy specimen. If the patient undergoes a surgical biopsy at TJU, the surgeon ([name]) will mark the transaxial plane of the lesion by sutures upon excision of the breast mass to allow additional data collection from this subgroup of patients in order to partially fulfill the secondary aim of this trial. At UCSD surgical biopsy specimens will be treated according to clinical standard i.e., the imaging plane and the pathology sections will not be matched.

## 6.6 Efficacy Assessments

The primary blinded read will be performed on all 450 human cases by a physician with more than 15 years of expertise in general breast imaging and with specific expertise in breast SHI ([name]). All imaging studies will be rated on a quasi-continuous scale from 0 to 100 ranging from “no lesion seen (no findings)” over “probably benign” and “indeterminate” to “malignant.” Using a quasi-continuous 100-point rating scale has an intuitive probabilistic interpretation and is known to improve the assessment of the characterization capabilities of the imaging modes studied [Wagner et al 2001].

The SHI images will be qualitatively analyzed as described above for the pulse inversion HI injection. The pre- and then post-contrast diagnostic US criteria (as detailed below) will be evaluated for each patient in two readings as follows: grayscale; grayscale and PDI (baseline); grayscale and contrast enhanced pulse inversion HI, and then in the second reading grayscale/baseline and SHI and, finally grayscale and SHI with dynamic CMI-SHI added. While this may introduce some bias from pre- to post-contrast results, we considered this the more realistic approach to how US contrast may be used in clinical practice. Moreover, such a “sequential” reading scheme may well produce the same total reader variance as a more independent reading scheme (where the evaluation of each imaging mode is separated in time by 1 month or more), while having the advantage of being logically much less demanding [Beiden et al 2002]. Each case will also be read by the two on-site investigators, blinded to the mammographic and histopathological diagnosis, to allow repeatability to be assessed for each site. Finally, each mammogram will be read by a radiologist as part of the patient’s standard clinical assessment and assessed using the BIRADS scale [ACR 1998].

Diagnostic US criteria (Evaluated for each imaging mode):

- Diagnosis; size, shape, and orientation of the lesion; echogenicity compared to surrounding tissue.

- Distribution of color signals and the overall color content of the lesion evaluated by comparing the pattern and amount of color to the normal surrounding breast.
  - If uniform, the color will be categorized as less intense, iso-intense or more intense than normal breast.
  - If non-uniform, the color will be described by location, intensity and distribution.
- Irregularity of the course of the vessels will be scored on a scale from 1.0 to 5.0 (smooth to severe irregularity)
- Anastomoses between adjacent vessels will be noted (as 1-2, 3-5 or >5 vessels connecting).
- Enhancement pattern will also be graded as peripheral, radial from one or multiple sites, spotty or a combination.

Sensitivity, specificity, accuracy, positive predictive value (PPV) and negative predictive value (NPV) will be calculated for all six imaging modalities (the five different US modes and mammography). The dichotomous parameter needed for these calculations will be derived by ascertaining whether the radiologist would recommend a biopsy or not based on the imaging study in question. Inter- and intra-observer variability will also be calculated

